#### **4.4.3.3 Exploratory Efficacy Variable 3**

The exploratory endpoint 3 will be change in mean VITA shade score from pre to post bleaching Treatment.

Descriptive statistics (n, missing, mean, SD, standard error [SE], median, minimum, and maximum) will be presented for mean VITA shade score at visit 2 (pre bleaching) and visit 3 (post bleaching) together with change from Visit 2 to Visit 3 will be presented in Table 14.2.4.3 for all subjects in the mITT population by study product group.

The results for this endpoint will be analyzed from an ANCOVA model where study product group will be fixed effect and mean VITA shade score prior to the start of tooth bleaching fitted as a covariate.

Using the above model, least squared mean, pairwise difference along with 95% CIs will be reported by study product in Table 14.2.4.4 for all subjects in the mITT population. Significance testing will be conducted at the two-sided 5% significance level.

The assumption of normality and homogeneity of variance in will be investigated. In case of violation of these assumptions, a suitable non-parametric test (Van Elteren) will be performed, and results will be provided to support the parametric results.

#### **4.4.4 Handling of Missing Values/Censoring/Discontinuations**

Missing data will not be replaced or imputed. Subjects who withdraw from the study prematurely will be included in the statistical analyses up to the point of discontinuation.

The use of repeated measures analyses accounts for missing data assuming a missing at random assumption, i.e., there is a systematic relationship between the propensity of missing values and the observed data, but not the missing data.

It is therefore assumed that a subject with missing data would have obtained a similar efficacy result compared to a subject using the same study product with similar non-missing results at other timepoints (Baseline and the other post-Baseline visit).

Sensitivity analyses may be added to the SAP prior to unblinding in case of high drop-out rates and/or exclusion from PP analyses.

#### **4.5 Analysis of Safety**

The safety profile of the study treatments will be assessed with respect to AEs or incidents or others such as OST/OHT abnormalities in oral health study and incidents related to medical devices.

#### **4.5.1 Adverse Events and Serious Adverse Events**

All AEs will be reviewed by the Clinical Research Scientist or Designee prior to database lock and will be coded to a system organ class (SOC) and preferred term (PT) using the Medical Dictionary for Regulatory Activities (MedDRA).

AEs will be classified as oral and non-oral on the AE page of eCRF.

Treatment emergent adverse events (TEAEs) are defined as new AEs that occur on or after the first study product use (if this date is missing a suitable alternative will be used e.g., date of randomization). AEs with an onset date/time prior to the first study product use will be considered as non-treatment emergent.

The following summary tables and listings will be presented by study product group.

- Table of All AEs (Table 14.3.1.1).
- Table of TEAEs by SOC and PT (Table 14.3.1.2).
- Table of TEAEs by Oral/Non-Oral and PT (Table 14.3.1.3)
- Table of treatment related TEAEs by SOC and PT (Table 14.3.1.4)
- Table of treatment related TEAEs by Oral/Non-Oral and PT (Table 14.3.1.5)
- Listing of all AEs (Listing 16.2.7.1 for all randomized subjects; Listing 16.2.7.2 for non-randomized subjects)
- Listing of deaths (Listing 14.3.2.1)
- Listing of non-fatal SAEs (Listing 14.3.2.2)
- Listing of TEAEs leading to study or product discontinuation (Listing 14.3.2.3)
- Listing of TEAEs classified as Oral (Listing 14.3.2.4)

In the event there is nothing to report, a null table or listing will be produced.

#### **4.5.2 Medical Device Incidents**

Medical device incidents involving an AE will be followed and reported in the same manner as other AEs. This applies to all subjects, including those who discontinue study product or are withdrawn from the study.

All reported incidents including onset date/time, outcome, end date/time, death date/time if any, treatment provided, reason of study withdrawn will be listed in Listing 16.2.7.3 for all Randomized subjects.

#### **4.5.3 Other Safety Variables**

Other safety variables are listed below:

- OST examination
- OHT examination

#### **4.5.3.1 OST Examination**

The OST examination will be accomplished by direct observation and palpation, using retraction aids as appropriate, and will include examination of the labial mucosa (including lips), buccal mucosa, mucogingival folds, gingival mucosa, hard palate, soft palate, tonsillar area, pharyngeal area, tongue, sublingual area, submandibular area and salivary glands. The results of the examination will be recorded in the eCRF as either 'normal' or 'abnormal'; with details of any abnormalities.

Any observation that changes from 'normal' to 'abnormal', or worsens, from the OST examination completed at Screening will be recorded as an AE.

OST will be summarized (number of subjects and percentages with abnormalities, without abnormalities, or OST not examined) by visit and study product in Table 14.3.4.1 for all subjects in the Safety Population. OST examination will be listed (Listing 16.2.8.1.1) with all records ('normal', 'abnormal' and 'not examined') for all randomized subjects, and a separate listing will be presented for 'abnormal' records only (Listing 16.2.8.1.2) for all randomized subjects.

#### **4.5.3.2 OHT Examination**

The OHT examination will be accomplished by direct observation, using retraction aids as appropriate, and will identify grossly carious lesions, signs of erosive wear, enamel irregularities, tooth fracture, gross generalized dental caries decay, decalcification and faulty restorations. The presence of any implants, fixed or removable dentures, fixed or removable orthodontic braces/bands, fixed orthodontic retainers, full crowns or veneers will be recorded. Observations will be listed as 'absent' or 'present'; conditions noted as 'present' will be described in the eCRF. Any observation that changes from 'absent' to 'present', or worsens, from the OHT examination completed at Screening will be recorded as an AE.

OHT examination will be listed (Listing 16.2.8.2) for all randomized subjects.

### **4.6 Analysis of Other Variables**

#### **4.6.1 Repeatability of the Tooth Color Assessment**

Approximately ten subjects will be randomly selected for repeat shade assessments at each assessment time point (Visits 1-5) to test the consistency of the examiner.

The repeat tooth stain assessments will be compared to the original assessments and will not be used in any efficacy analysis. The first and second assessments on each tooth site will be cross tabulated. A weighted Kappa coefficient ( $\kappa$ ), along with the 95% CI will be calculated to assess the intra-examiner reliability in Table 14.2.5.1 for all subject in VITA Shade repeatability population by study Product Group. Fleiss-Cohen weighted kappa will be calculated for the repeatability analysis. Reliability will be deemed-

- Excellent if  $\kappa > 0.75$

- Fair-to-good if  $0.4 \leq \kappa \leq 0.75$
- Poor if  $\kappa < 0.4$

All subjects who have repeatability data will be included in this analysis. If the same subject is selected at random for repeatability assessments at multiple visits, the pairs of observations will be considered as independent for the purposes of repeatability analysis; that is, any potential with subject correlation will be ignored.

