#### 9.2.1 Tooth Color Assessment

Tooth color of the facial surfaces of the six anterior maxillary teeth (tooth numbers 6-11) [Universal tooth numbering system] will be assessed by a single, trained clinical examiner using the VITA Bleachedguide 3D-MASTER. The arch tooth position will be parallel to the floor.

Assessment conditions should be standardized: color corrected lighting in the range of 5000° Kelvin; a grey bib will be placed over the subject's clothing; subjects will be asked not to wear lipstick; assessments will be performed in the same room (necessary) at approximately the same time of day (if possible); outside light will be controlled by covering the windows or using a windowless room. Color determination should be made within 5-7 seconds of starting an assessment to avoid eye fatigue.

The VITA Bleachedguide 3D-MASTER ([Paravina, 2008](#)) uses a value-ranked ordered scale from 1 (the lightest) to 29 (the darkest). The shade level of each tooth surface is scored visually by the clinical examiner with reference to the Bleachedguide.

A single VITA Bleachedguide 3D Master Shade guide will be used for all assessments throughout the study wherever possible.

Subjects should have abstained from all oral hygiene procedures (including tooth brushing) for at **least 6 hours** prior to and during this assessment. Additionally, subjects should have refrained from eating or drinking for at **least 2 hours** prior to and during this assessment, with the exception of small amounts of water required for taking medication.

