### 9.2.1.1 Repeatability of the Tooth Color Assessment

To assess the repeatability of the tooth color assessments, replicate examinations will be performed by the same clinical examiner using the same VITA Bleachedguide 3D Master shade guide. Approximately ten subjects will be randomly selected for repeat shade assessments at each assessment time point (Visits 1-5), a total of 50 repeat shade assessments over the duration of the study. Replicate assessments will be separated by a minimum of 10 minutes (maximum 60 minutes) from the original assessment for a given subject and, where possible, separated by at least one subject.

The scores of the initial assessment will not be visible to the examiner or scribe when the repeat assessment is carried out.

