### 9.2.2 Macpherson Modification of the Lobene Stain Index (MLSI)

Extrinsic dental stain will be assessed on the facial surfaces of the 6 maxillary anterior teeth (6-11) [Universal tooth numbering system] at Visits 1-5), using the MacPherson modification ([Macpherson et al., 2000](#)) of the Lobene stain index ([Lobene, 1968](#)) (MLSI).

[figure not shown]
All assessments should be performed by a single, trained clinical examiner, with consistent lighting to standardize of the assessment conditions. If required, the examiner will brush the subject's anterior teeth with a wetted toothbrush and/or floss to remove any debris which could impact the accuracy of the stain assessment. Teeth will be air dried prior to and during the assessment as needed.

The facial surfaces of each assessable tooth is divided into four regions. The 'gingival' region is defined as a crescent-shaped band, approximately 2 mm wide, adjacent to the free margin of the gingiva and extending to the crest of the interdental papillae of the adjacent teeth. The 'body' of the tooth is then sub-divided into three regions on the facial surfaces.

The facial surfaces of each assessable tooth will be divided into 2 regions, with a total of 4 sites per tooth surface ([Figure 9-1](#)).

- **Gingival Region:** Defined as a crescent-shaped band (~ 2 mm wide) adjacent to the free margin of the gingiva and extending to the crest of the inter-dental papillae of the adjacent teeth (1 site).
- **Body Region:** The remainder of the tooth surface (the body) is further sub-divided into 3 sites.
  - Distal facial, body facial, mesial facial sites
  - Distal lingual, body lingual, mesial lingual sites

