### 9.2.2.1 Repeatability of the MLSI Assessment

To assess the repeatability of the MLSI assessments, replicate examinations will be performed by the same clinical examiner. Approximately ten subjects will be randomly selected for repeat MLSI assessments at each assessment time point (Visits 1-5), a total of approximately 50 repeat assessments over the duration of the study. Replicate assessments will be separated by a minimum of 10 minutes (maximum 60 minutes) from the original assessment for a given subject and, where possible, separated by at least one subject.

The scores of the initial assessment will not be visible to the examiner or scribe when the repeat assessment is carried out.

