## 12.3 Statistical Analyses

Additional details of the proposed statistical analysis will be documented in the statistical analysis plan (SAP), which will be written following finalization of the protocol and prior to study unblinding/analysis (as appropriate). This section is a summary of the planned statistical analyses for the primary and key secondary endpoints.

The mITT population will be used for all efficacy analyses. No repeat assessment data is to be used in any efficacy analyses.

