#### **12.3.5 Other Analyses**

The repeat tooth stain and color assessments will be compared to the original assessments and will not be used in any efficacy analysis. The first and second assessments on each tooth site

Property of Haleon- Confidential

May not be used, divulged, published or otherwise disclosed without the consent of Haleon

will be cross tabulated. A weighted Kappa coefficient ( $\kappa$ ), along with the 95% CI will be calculated to assess the intra-examiner reliability. Fleiss-Cohen weighted kappa will be calculated for the repeatability analysis. Reliability will be deemed-

- Excellent if  $\kappa > 0.75$
- Fair-to-good if  $0.4 \leq \kappa \leq 0.75$
- Poor if  $\kappa < 0.4$

All subjects who have repeatability data will be included in this analysis.

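### The repeatability kappa intervals make no allowance for teeth and sites sharing a mouth, so they are too narrow if scores within a mouth are positively correlated

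*SAP*

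**What the plan says.** Protocol 9.2.1.1 and 9.2.2.1 have the same examiner repeat the assessment on about ten randomly chosen subjects at each of Visits 1-5: "a total of 50 repeat shade assessments over the duration of the study" for shade, and "a total of approximately 50 repeat assessments over the duration of the study" for stain. Shade is scored on six maxillary teeth (Protocol 9.2.1). MLSI is scored on the same six teeth, "with a total of 4 sites per tooth surface" (Protocol 9.2.2).

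Protocol 12.3.5 plans a weighted kappa, "along with the 95% CI will be calculated to assess the intra-examiner reliability". SAP 4.6.1 (shade) and 4.6.2 (MLSI) carry this forward with Fleiss-Cohen weights, by product group. Both take the tooth or site as the unit: "The first and second assessments on each tooth site will be cross tabulated". Their only statement on dependence concerns a subject who happens to be drawn at more than one visit. Those pairs are to be taken as independent, and "any potential with subject correlation will be ignored". Neither document says how the variance of kappa is to be estimated, and neither mentions the several pairs that come from one mouth at one sitting.

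**The concern.** The number of pairs is far larger than the number of mouths. One examiner scores all six teeth of a subject by eye in one sitting, one tray bleaches the upper teeth together, and visits before and after bleaching are pooled. Positive correlation within a mouth is therefore plausible, although the documents do not quantify it. An interval that counts each tooth or site as an independent observation then claims more information than about 25 mouths can supply.

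This is the only reliability analysis planned for the single examiner whose visual score is the primary endpoint, and SAP Appendix 1 marks both tables (14.2.5.1 and 14.2.5.2) for topline. What is at stake is how precisely reliability appears to have been shown. Nothing else moves: Protocol 12.3 states that "No repeat assessment data is to be used in any efficacy analyses", and the Excellent / Fair-to-good / Poor grade uses kappa itself, not its interval.

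**Working it through.** **1. The plan's own figure.** 10 subjects x 5 visits = 50 repeat examinations, as stated in Protocol 9.2.1.1. No kappa, standard error or interval width is given anywhere.

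**2. Pairs and mouths.** VITA: 50 x 6 = 300 pairs. MLSI: 50 x 6 x 4 = 1200 pairs. Assuming an even split by product, there are 25 examinations per group, giving 150 and 600 pairs. With 5 of 80 subjects drawn per group at each visit, the expected number of distinct subjects per group is 80 x (1 - (75/80)^5) = 22.1.

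**3. Closed form.** For a quadratic-weighted kappa under normality with m pairs per mouth, the design effect is

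DE = 1 + (m - 1)(rs² + rd²)/2,

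where rs and rd are the within-mouth correlations of the pair sums and pair differences. Correlated true scores raise DE even if the examiner's errors are independent (rd = 0), because kappa depends on the spread of scores, and that spread is then estimated from few mouths.

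Example (assumed values): true-score correlation 0.5 and single-score reliability 0.8. Error variance is 0.2/0.8 = 0.25 of true variance, so rs = 0.5 x 4/4.5 = 0.444.

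- VITA, m = 6: DE = 1 + 5 x 0.444²/2 = 1.49; SE ratio √1.49 = 1.22.
- MLSI, m = 24: DE = 1 + 23 x 0.444²/2 = 3.27; SE ratio √3.27 = 1.81 on a continuous scale.

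**4. Simulation by correlation.** 25 distinct mouths, 2,000 runs per setting, reliability 0.8, VITA true-score SD 3, MLSI as a 0-3 score with illustrative cut-points. The ratio is the true SD of kappa over the mean plain SE. Coverage of the nominal 95% interval is shown as plain / clustered on subject.

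| True-score correlation | VITA ratio | VITA coverage % | MLSI ratio | MLSI coverage % |
|---|---|---|---|---|
| 0 | 1.02 | 94.6 / 94.9 | 0.99 | 94.6 / 94.8 |
| 0.2 | 1.05 | 93.2 / 94.4 | 1.10 | 92.6 / 94.6 |
| 0.5 | 1.24 | 89.3 / 94.4 | 1.53 | 79.9 / 92.6 |
| 0.8 | 1.59 | 78.9 / 93.2 | 2.27 | 61.3 / 89.8 |
| 0.5, with error correlation 0.2 | 1.33 | 86.4 / 94.4 | 1.62 | 76.6 / 92.0 |

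The plain interval is sound at zero correlation and too narrow at every positive value tried. For VITA the 1.24 agrees with the closed form. The MLSI ratio is below its closed-form value because coding into four categories weakens the correlation.

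**5. Simulation over variance components, with subjects redrawn across visits.** 5 of 80 per group per visit, 4,000 runs per setting, plain delta-method SE. All components are assumptions.

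- VITA (scores 1-29, mean 18, shift 0 or 4 at Visits 3-5), SDs for subject/tooth/session/residual: 1.2/0.8/1.0/1.0; 1.2/0.8/0.7/1.22; 1.2/0.8/0/1.41; 1.4/1.0/0.85/0.85; 2.0/1.2/0.8/0.8; 2.0/1.2/0.55/1.0; 0.8/1.4/0/1.2; 0.8/1.4/0.3/1.0; 0.5/1.5/0/1.2; 1.0/1.0/0.5/1.0. Ratio 1.06-1.88, coverage 72.0-93.3%.
- MLSI (cut-points 0/0.8/1.6, latent mean 0, 0.4 or 0.8), SDs for subject/tooth/site/session/residual: 0.7/0.5/0.5/0.4/0.4; 0.7/0.5/0.5/0.28/0.49; 0.7/0.5/0.5/0/0.57; 0.6/0.4/0.5/0.55/0.55; 0.4/0.4/0.7/0.1/0.5; 0.3/0.3/0.8/0/0.5; 0.5/0.4/0.6/0.2/0.5. Ratio 1.06-2.32, coverage 60.4-93.4%.
- All 25 subjects distinct: VITA 1.02-1.84 (73.1-94.6%), MLSI 1.02-2.25 (61.2-94.4%).
- Control without subject or session variance: 1.02-1.05 (92.5-94.6%).

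A separate simulation of nine of these settings gave 1.08-1.81 for VITA and 1.05-2.33 for MLSI.

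**6. Source of the effect.** In the third MLSI setting the ratio is 1.71-1.72 with redraws and 1.56-1.57 with distinct subjects; 1.71/1.56 = 1.10. Redrawing subjects across visits adds at most about that factor. Where the ratio is large, teeth or sites within a mouth are the main cause.

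**The case against.** The strongest reply is that nothing depends on this interval. No minimum kappa, test of kappa or action on poor reliability is specified, and repeat data never enter an efficacy analysis. That stands, and it caps the point at minor.

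The cross-visit independence is openly declared. True, but it is the small part; the SAP is silent on the larger part, clustering within a mouth.

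The SAP does not name the plain asymptotic standard error; it is inferred. The inference is fair: pairs are cross-tabulated by tooth or site, independence is asserted for repeat draws, and nothing else is offered.

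The size rests wholly on assumptions, and its low end (1.06, or 1.02 with distinct subjects) barely differs from the 1.02-1.05 seen with no subject or session variance. This also stands. The low end should not be credited to clustering.

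Three inputs are approximations. The draw is not balanced by product. Visit 1 shade and stain are scored before randomization, so a repeated subject who then fails screening has no product group. The calculation also ignores the planned 20% dropout. In addition, SAP 4.6.2 does not say whether area, intensity or their product is tabulated. Only a 0-3 score was simulated, so the MLSI range is not shown to hold for the product. None of this changes the direction.

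**Conclusion.** The concern holds, as a minor one. As written, the plan leads to a 95% interval that is too narrow whenever scores within a mouth are positively correlated. Under the assumed components the true standard error is 1.06-1.88 times the plain one for VITA and 1.06-2.32 times for MLSI. The low end arises when most variation lies between teeth or sites, the high end when subject or sitting effects are large. Confidence in the direction is high; confidence in the size is only moderate, since it rests on assumed variance components, about 25 examinations per group and a 0-3 MLSI score. The kappa estimates, their grades and every efficacy result are unaffected.

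**What to change.** In SAP 4.6.1 and 4.6.2, replace the sentence that treats repeat pairs as independent with:

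> The 95% CI will use a cluster-robust variance with the subject as the unit, within product group, keeping all teeth or sites and all visits of a subject together, with t quantiles on (number of subjects - 1) degrees of freedom.

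The kappa, the grade cut-offs and the split by product stay as planned.

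In the settings of step 5 this interval covered 91.9-95.1% for VITA and 91.5-95.1% for MLSI. It can still fall slightly short: with 25 mouths, 24 sites and correlation 0.8 (step 4) it covered about 90%. A percentile bootstrap resampling whole subjects within product group is a possible alternative, but it covered less well (87-94% for VITA, 89-94% for MLSI; 400 runs), so the cluster-robust interval should be the default.

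The cost is a short program and one sentence per section, with no new data. The reported interval becomes 1.09-1.79 times as wide for VITA and 1.12-2.32 times for MLSI under the same assumptions. Part of this is the t quantile: with 21 degrees of freedom, 2.08/1.96 = 1.06.

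### Pooling repeat shade pairs across pre- and post-bleach visits raises the quadratic-weighted kappa above within-visit reliability; the split by product separately costs precision

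*SAP*

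**What the plan says.** Protocol 9.2.1.1 plans replicate shade scoring by the same examiner on about ten subjects at each of the five visits, "a total of 50 repeat shade assessments over the duration of the study". SAP 4.6.1 sets out the analysis:

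- The unit is the tooth: "The first and second assessments on each tooth site will be cross tabulated".
- The statistic has quadratic weights: "Fleiss-Cohen weighted kappa will be calculated for the repeatability analysis". A 95% CI accompanies it.
- It is reported "for all subject in VITA Shade repeatability population by study Product Group". No split by visit or bleaching phase is stated.
- On repeated selection: "If the same subject is selected at random for repeatability assessments at multiple visits, the pairs of observations will be considered as independent".
- A verbal grade follows: excellent above 0.75, fair-to-good from 0.4 to 0.75, poor below 0.4.

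The SAP never states that visits are pooled, and the shell for Table 14.2.5.1 is only named. Pooling is still the clear reading. Everyone with repeat data enters the analysis, and the independence rule has no purpose unless visits are combined. Where the SAP wants a visit split it says so, as for the soft-tissue table in 4.5.3.1: "by visit and study product in Table 14.3.4.1".

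Protocol 12.3.5 specifies the same kappa and bands without mentioning a split by product. SAP 4.6.2 repeats the scheme for the MLSI.

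**The concern.** For a fixed examiner error, quadratic-weighted kappa rises with the spread of the true scores. Visits 1-2 precede bleaching, with an entry rule of mean shade at least 13. Visits 3-5 follow a treatment meant to lighten teeth. Combining them adds the pre/post shift to the spread while the examiner's error stays the same. The primary comparison is between products at Week 24, where that shift is absent.

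At stake is how the reliability of the primary measurement is described. Table 14.2.5.1 is marked as a topline output, and a reader may take its grade as describing how well the examiner separates subjects at Week 24.

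Two further points arise. Splitting by product divides a small sample to estimate a property of a single blinded examiner. Treating all pairs as independent ignores clustering of six teeth, and possibly several visits, within a subject, which will tend to make the confidence interval too narrow.

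**Working it through.** **The plan's own figure.** 10 subjects × 5 visits = 50 repeat assessments, as stated. Of these, 20 (40%) fall before bleaching and 30 (60%) after. By product, 50 / 2 = about 25 subject-visits per group.

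**Formula.** If the two readings have equal mean and variance, quadratic-weighted kappa = 1 − e²/s², where e² is the examiner error variance and s² the observed within-visit variance. So e² = (1 − kw)s², with kw the within-visit kappa. Pooling adds a between-visit variance B:

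pooled kappa = (kw·s² + B) / (s² + B)

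For a single pre/post shift of D shades with p = 0.4 before bleaching, B = p(1 − p)D² = 0.24·D².

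**Assumed inputs.** The documents give no expected shift, tooth-level SD, examiner error or kappa. Their only SD is 2, a subject-level planning value for VITA change in SAP 1.4. It is borrowed here as one assumption for s, with 3 and 4 as alternatives.

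**Effect at kw = 0.60, s = 2** (kw·s² = 2.4, s² = 4):

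- D = 2: (2.4 + 0.96)/(4 + 0.96) = 0.68
- D = 3: (2.4 + 2.16)/(4 + 2.16) = 0.74
- D = 4: (2.4 + 3.84)/(4 + 3.84) = 0.80

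**Shift at which pooled kappa reaches 0.75.** Solving gives D = s·√[(0.75 − kw)/(0.25 × 0.24)] = s·√[(0.75 − kw)/0.06].

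| kw | s = 2 | s = 3 | s = 4 |
|---|---|---|---|
| 0.40 | 4.8 | 7.2 | 9.7 |
| 0.50 | 4.1 | 6.1 | 8.2 |
| 0.60 | 3.2 | 4.7 | 6.3 |
| 0.70 | 1.8 | 2.7 | 3.7 |

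**Simulation check.** This used the integer 1-29 scale, six teeth, the entry rule at Visits 1-2 and partial relapse after bleaching. Assumed values were a pre-bleach mean of 17, subject SD 1.4, tooth SD 0.8 and examiner error SD 1.2 or 1.4.

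| Shift at Visits 3/4/5 | Pooled, within-visit 0.63 | Pooled, within-visit 0.56 |
|---|---|---|
| 0/0/0 | 0.63 | 0.56 |
| 2/1.5/1 | 0.68 | 0.61 |
| 3/2.5/2 | 0.73 | 0.67 |
| 4/3/2 | 0.77 | 0.72 |
| 5/4/3 | 0.82 | 0.77 |

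**Product split.** Take kw = 0.60, s = 2 and shifts of 4.5 and 3.5 in the two arms. Separately, B = 0.24 × 4.5² = 4.86 gives 7.26/8.86 = 0.82, and B = 0.24 × 3.5² = 2.94 gives 5.34/6.94 = 0.77. Combined, B = 3.99 gives 6.39/7.99 = 0.80. The split does not inflate. Its cost is precision: with 25 subject-visits, the simulated 95% range of pooled kappa was about 0.66 to 0.84 at shifts 4/3/2 and within-visit 0.63, which straddles the cut.

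**The case against.** The strongest reply is that nothing depends on the grade. Repeat data enter no efficacy analysis, success is defined by significance at 24 weeks, and no rule acts on kappa. The cross-tabulation also leaves raw disagreement visible. All of this stands, and it limits the point to labelling and precision.

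Next, reliability over the full range is a legitimate target. The guide is also used across the shift: the Visit 2 to Visit 3 change is an exploratory endpoint and the primary model includes Visits 2-5. The pre-bleach stratum is itself range-restricted by the entry rule, which tends to depress kappa. This also stands. It argues for showing both values, and against resting the grade on the post-bleach value alone.

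Four stronger readings might be inferred, and the documents do not support them:

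- **That the product split helps inflate kappa.** The arithmetic above shows it does not.
- **That an examiner who only tells bleached from unbleached teeth could be graded excellent.** Assume visit means of 17, 17, 10, 11, 12, so B = 9.04, and true within-visit variance 2² + 1.5² = 6.25. With no within-visit discrimination, pooled kappa is about 9.04/(6.25 + 9.04) = 0.59, still fair-to-good. Reaching 0.75 from zero needs a shift of about √(0.75/0.06) = 3.5 within-visit SDs.
- **That the grade will change.** With that true variance of 6.25 and smaller assumed shifts (means 17, 17, 12, 13, 14; B = 4.24), observed within-visit variance is 6.25/kw. A kappa of 0.65 becomes (6.25 + 4.24)/(9.62 + 4.24) = 0.76, but 0.58 becomes 10.49/(10.78 + 4.24) = 0.70 and keeps its grade.
- **That MLSI kappa is inflated in the same way.** The MLSI scores extrinsic stain from 0 to 3, whereas Protocol section 2 describes bleaching as acting on chromophores within the tooth. No MLSI shift is given or shown.

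**Conclusion.** The point holds as a minor one. On the clear, though inferred, reading that visits are pooled, any non-zero bleaching shift makes the tooth-color kappa in SAP 4.6.1 larger than the within-visit reliability relevant at Week 24.

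A move from fair-to-good to excellent is possible but conditional. For within-visit kappa from 0.70 down to 0.40, it needs a shift of roughly 1.8 to 4.8 shades at SD 2, or 2.7 to 7.2 at SD 3. It cannot occur if within-visit kappa already exceeds 0.75. These thresholds rest on the intraclass-correlation approximation, a 40/60 split of repeats and assumed SDs.

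The product split is a separate matter of precision. The independence rule is the evidence for pooling; its own direct effect is mainly on the width of the interval. A reader might infer that the primary result is in doubt, but no efficacy estimate or test uses these data.

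**What to change.** 1. In SAP 4.6.1 and 4.6.2, compute kappa over both products combined. This agrees with Protocol 12.3.5, which mentions no product split.
2. For tooth color, report kappa for Visits 1-2 and for Visits 3-5 beside the pooled value, and state which visits each covers, so that the grade is not read from the pooled figure alone. Relapse across Visits 3-5 would leave some residual inflation. With assumed means 10, 11, 12, B = 0.67, and at s = 2 a kappa of 0.60 becomes (2.4 + 0.67)/(4 + 0.67) = 0.66.
3. Replace the independence rule with a confidence interval that allows for clustering of teeth and visits within subject, for example a bootstrap that resamples subjects.

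The same edit can correct 4.6.1, which refers to repeat stain assessments, and 4.6.2, which refers to repeat color assessments; the two appear to be swapped.

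The cost is SAP wording, table layout and a little programming. The downside is a wider interval per phase and possibly a less favourable grade. No data collection or efficacy analysis changes.
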